 - Subjects who are on monotherapy with oral antidiabetic agent at Baseline
 - Subjects with early T2DM (duration of diagnosis of diabetes is less than 5 years) at Baseline.
- Proportions of subjects with prediabetes at Baseline who develop new diagnosis of diabetic retinopathy or new diagnosis of diabetic neuropathy by EOS (revised per Amendment 01)
- Proportions of subjects with T2DM at Baseline who develop new diagnosis of diabetic retinopathy or new diagnosis of diabetic neuropathy by EOS (revised per Amendment 01)

Analysis Sets

The Safety Analysis Set will be the group of subjects who received at least 1 dose of study drug and had at least 1 postdose safety assessment.

The Intent-to-Treat set (ITT) will be the group of all randomized subjects regardless of whether they took study drug or not.

- Total Time Analysis Set: Using the ITT, events are counted that occur while subjects are on and off treatment. Subjects with no events who discontinue early or complete the study will be censored at their last study contact (see details in the SAP). This will be used for the primary analysis.
- On-Treatment plus 30 Days Analysis Set: Using the ITT, events are counted that occur while subjects are on treatment and up to 30 days from their last dose. Subjects with no events who discontinue early or complete the study will be censored at their last dose day plus 30 days.
- On-Treatment Analysis Set: Using the ITT, events are counted that occur while subjects are on treatment. Subjects with no events who discontinue early or complete the study will be censored at their last dose day.
- Prediabetes Analysis Set: This set includes all subjects in the ITT set without a history of any type of diabetes and who are prediabetic at Baseline. Definition of prediabetes will be found in the SAP. (revised per Amendment 01)
- Nondiabetes Analysis Set: This set includes all subjects in the ITT set without a history of any type of diabetes at Baseline. Definition of nondiabetes will be found in the SAP. (revised per Amendment 01)

T2DM Analysis Set: This set will be all subjects in the ITT who have T2DM at Baseline.

FDA-defined Valvulopathy Analysis Set: This set will be all subjects in the ITT without FDA-defined valvulopathy at Baseline. The data from this study will be pooled with the data from the 3 pivotal lorcaserin HCl studies (APD356-009, -010, and -011).

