- The time-to-event of each component of MACE+. The Total Time Analysis Set will be used as the primary analysis. The On-Treatment Analysis Set and the On-Treatment plus 30 Days Analysis Set will be used as sensitivity analyses.
- Time-to-event of all-cause mortality. The Total Time Analysis Set will be used as the primary analysis. The On-Treatment Analysis Set and the On-Treatment plus 30 Days Analysis Set will be used as sensitivity analyses.
- Time-to-event of new onset renal impairment or worsening existing renal impairment in all subjects. The ITT Analysis Set will be used for this analysis. (revised per Amendment 02)
- Time-to-event of new onset renal impairment or worsening existing renal impairment in subjects with T2DM at Baseline. The T2DM Analysis Set will be used for this analysis.
- Time-to-event of new onset renal impairment or worsening existing renal impairment in subjects with prediabetes at Baseline. The Prediabetes Analysis Set will be used for this analysis. (revised per Amendment 01)
- Time-to-event of improvement in renal function. The T2DM Analysis Set will be used for this analysis.
- Time-to conversion to T2DM in subjects without any type of diabetes at Baseline. The Nondiabetes Analysis Set will be used for this analysis. (revised per Amendment 01)
- Time to conversion to normal glucose homeostasis ($HbA_{1c} \leq 5.6\%$ and fasting plasma glucose < 100 mg/dL without any antidiabetic treatment). The Prediabetes Analysis Set will be used for this analysis. (revised per Amendments 01 and 02)
- Change from Baseline in HbA_{1c} at 6 months in subjects with T2DM at Baseline will be analyzed using an analysis of covariance (ANCOVA) model with treatment and stratification variable (presence of established CV disease or CV risk factors without established CV disease) as factors, and baseline HbA_{1c} , as a covariate. Comparison between lorcaserin HCl and placebo will be made at 6 months. The estimated treatment difference between lorcaserin HCl and placebo and the 2-sided 95% CI will be calculated. The

T2DM Analysis Set will be used for this analysis. (revised per Amendment 01)

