- The proportion of subjects who meet FDA-defined valvulopathy in echocardiographically determined heart valve changes will be analyzed using logistic regression including treatment as a factor and baseline BMI as a covariate. Comparison between lorcaserin HCl and placebo will be made at 1 year. The FDA-defined Valvulopathy Analysis Set will be used for this analysis.
- The proportion of subjects with FDA-defined valvulopathy at Baseline who demonstrate worsened FDA-defined valvulopathy at 1 year will be analyzed using logistic regression including treatment as a factor and baseline BMI as a covariate. A comparison between lorcaserin HCl and placebo will be made at 1 year. The ITT analysis set in subjects with FDA-defined valvulopathy at Baseline will be used for this analysis. (revised per Amendment 01)
- The change from Baseline in echocardiographically-determined pulmonary arterial systolic pressure will be analyzed using a mixed-effects model with repeated measures with treatment as a factor and baseline BMI as a covariate. Comparison between lorcaserin HCl and placebo will be made at 1 year and the corresponding 2-sided 95% CI will be calculated. The ITT will be used for this analysis. (revised per Amendment 01)

Exploratory Endpoint Analyses

- The change from Baseline in CV risk factors (body weight, BMI, waist and hip circumference, dyslipidemia, insulin level, hypertension, inflammatory biomarkers) will be analyzed using a mixed-effects model with repeated measures with treatment and stratification variable (presence of established CV disease or CV risk factors without established CV disease) as factors. Comparison between lorcaserin HCl and placebo will be made at 1 year. The ITT will be used for this analysis.
- For subjects with NAFLD at Baseline, the change from Baseline in LFTs (AST, ALT, alkaline phosphatase, GGT, total and direct bilirubin) will be analyzed using a mixed-effects model with repeated measures with treatment and stratification variable (presence of established CV disease or CV risk factors without established CV disease) as factors. Comparison between lorcaserin HCl and placebo will be made at 1 year. The ITT will be used for this analysis.

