Phase	Pre-randomization	Randomization																		
Period	Screening	Treatment																	F/U	
Visit	1	2 ^a	3	4	5	6	7	8	9	10	11	12	13	14	15	16	17	EOT	EOS	Unsch ^b
Month ^c	Days -30 to -1	Day 1	3	6	9	12	15	18	21	24	28	32	36	40	44	48	52	56		
Assessment (revised per Amendment 01)																				
Study drug dispensing ^e		X	X	X	X	X	X	X	X	X	X	X	X	X	X	X	X	X		
Collect study medication ^e			X	X	X	X	X	X	X	X	X	X	X	X	X	X	X	X	X	
Drug accounting & compliance ^e			X	X	X	X	X	X	X	X	X	X	X	X	X	X	X	X	X	
AE monitoring ⁱ	<----->																			
MACE/MACE+ reporting ⁱ	<----->																			

(revised per Amendment 01)

Notes: Upon Sponsor Notification of Study Completion (ie, trial completion), sites will be instructed to bring subjects who remain on treatment for an EOT visit. An EOS visit will occur approximately 30 days later for subjects on treatment at Sponsor Notification of Study Completion.

Subjects who prematurely discontinue study drug are to complete the EOT visit within approximately 30 days, and will continue in the study for all subsequent study visits until study completion. If the next scheduled visit after EOT assessments is <30 days, subjects can skip that visit and return for the next subsequent visit (eg, if the EOT is 15 days prior to the scheduled Month 36 visit, they can skip Month 36, and come in at Month 40). All procedures and assessments should be performed at subsequent visits until EOS except where footnoted in assessment column. Upon Sponsor Notification of Study Completion, subjects who prematurely discontinued study medication ≥30 days before will return for an EOS visit. Subjects who are still being followed in the study but who discontinued study medication within 30 days of Sponsor Notification of Study Completion will return for an EOS visit approximately 30 days after their last dose of study medication.

ACR = albumin-to-creatinine ratio; AE = adverse event, ECG = electrocardiogram, EOS = end of study; EOT = end of treatment; F/U = Follow-up; HbA_{1c} = glycosylated hemoglobin, hsCRP = high sensitivity C-reactive protein; incl. = including; IxRS = interactive voice and/or web response system; MACE = major adverse cardiovascular events; MACE+ = MACE or hospitalization for unstable angina or heart failure, and any coronary revascularization; PGx = pharmacogenomics, Unsch = unscheduled.

- a. Visit 2 = Baseline/Randomization. The first dose should be taken at this visit. (revised per Amendment 01)

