- b. Assessments are only to be performed if clinically indicated or necessary due to state controlled substance requirements. (revised per Amendment 01)
- c. Window ±10 days for all visits after Visit 2, other than the EOS visit which has a window of +10 days. Month is shown unless otherwise indicated; 1 month = approximately 30 days.
- d. Only for a subset of subjects at selected sites. Baseline echocardiograms will be performed in between Visits 1 and 2, after the results of screening assessments have been obtained but prior to randomization, and subject eligibility is confirmed. ECHOs will be performed until at least 1000 subjects have completed the Month 36 echocardiographic assessment. (revised per Amendment 02)

Table 4 Schedule of Procedures/Assessments in Study APD356-G000-401

Phase	Pre-randomization	Randomization																		
Period	Screening	Treatment																	F/U	
Visit	1	2 ^a	3	4	5	6	7	8	9	10	11	12	13	14	15	16	17	EOT	EOS	Unsch ^b
Month ^c	Days -30 to -1	Day 1	3	6	9	12	15	18	21	24	28	32	36	40	44	48	52	56		
Assessment (revised per Amendment 01)																				

- e. For subjects who discontinue study drug early, these assessments will be stopped after the EOT visit.
- f. Renal function parameters and glycemic profile should be obtained at all specified visits, regardless of study drug status. (revised per Amendment 01)
- g. Serum cystatin C will be measured at Baseline and yearly thereafter in the subpopulation with CKD Stage 1 or 2 at Baseline. Serum creatinine will be measured in chemistry blood samples if chemistry assessments are performed.
- h. Serum pregnancy tests will be conducted at Screening. A urine pregnancy test will be conducted at randomization.
- i. These assessments should be done if a telephone contact is performed in lieu of a clinic visit.

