9.7.1.2 Definitions of Analysis Sets

The Safety Analysis Set will be the group of subjects who received at least 1 dose of study drug and had at least 1 postdose safety assessment.

The Intent-to-Treat set (ITT) will be the group of all randomized subjects regardless of whether they took study drug or not.

- Total Time Analysis Set: Using the ITT, events are counted that occur while subjects are on and off treatment. Subjects with no events who discontinue early or complete the study will be censored at their last study contact (see details in the SAP). This will be used for the primary analysis.
- On-Treatment plus 30 Days Analysis Set: Using the ITT, events are counted that occur while subjects are on treatment and up to 30 days from their last dose. Subjects with no events who discontinue early or complete the study will be censored at their last dose day plus 30 days.
- On-Treatment Analysis Set: Using the ITT, events are counted that occur while subjects are on treatment. Subjects with no events who discontinue early or complete the study will be censored at their last dose day.
- Prediabetes Analysis Set: This set includes all subjects in the ITT set without a history of any type of diabetes and who are prediabetic at Baseline. Definition of prediabetes will be found in the SAP. (revised per Amendment 01)
- Nondiabetes Analysis Set: This set includes all subjects in the ITT set without a history of any type of diabetes at Baseline. Definition of nondiabetes will be found in the SAP. (revised per Amendment 01)

T2DM Analysis Set: This set will be all subjects in the ITT who have T2DM at Baseline.

FDA-defined Valvulopathy Analysis Set: This set will be all subjects in the ITT without FDA-defined valvulopathy at Baseline. The data from this study will be pooled with the data from the 3 pivotal lorcaserin HCl studies (APD356-009, -010, and -011).

The PD Analysis Set will be the group of subjects who have both baseline and at least 1 postbaseline assessment of at least 1 PD parameter.

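### The echo safety comparisons are ITT-based and include echoes taken after study drug was stopped, with no exposure-based comparison beside them

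*Protocol*

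**What the plan says.** **Analysis sets.** For new valvulopathy, the protocol Synopsis says: "Comparison between lorcaserin HCl and placebo will be made at 1 year. The FDA-defined Valvulopathy Analysis Set will be used for this analysis". It defines that set thus: "This set will be all subjects in the ITT without FDA-defined valvulopathy at Baseline". For worsened valvulopathy it says: "The ITT analysis set in subjects with FDA-defined valvulopathy at Baseline will be used for this analysis". Change in pulmonary artery systolic pressure uses the ITT. Protocol 9.7.1.2 says that the ITT "will be the group of all randomized subjects regardless of whether they took study drug or not". The later-year exploratory echo analyses (protocol 9.7.1.8, SAP 5.8) use the same kinds of set. SAP 5.4.3 repeats the 1-year analyses and adds only a pooled repeat with the three pivotal studies. SAP 5.4.4 is a weight or BMI association model, not a treatment comparison by exposure.

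**Echoes after stopping.** The notes to protocol Table 4 say of subjects who stop drug early: "All procedures and assessments should be performed at subsequent visits until EOS except where footnoted in assessment column". The footnote that ends assessments is (e): "For subjects who discontinue study drug early, these assessments will be stopped after the EOT visit". The echocardiogram row carries footnote (d) only, so echoes go on. This was deliberate, because the Version 5.0 entry in the revision history gives continued echo as the reason for taking footnote (e) off that row.

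**Other endpoints.** For MACE+ components and all-cause mortality the protocol adds: "The On-Treatment Analysis Set and the On-Treatment plus 30 Days Analysis Set will be used as sensitivity analyses". MACE, MACE+ and T2DM conversion have the same provision (protocol 9.7.1.6, SAP 5.4.1 and 5.4.2).

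**The concern.** These are harm endpoints. Protocol 9.5.1.5 says the images are acquired to establish cardiac safety, and 9.5.3 says the serial echoes are there because FDA required them. ITT is a sound primary analysis. For harm, though, mixing in subjects no longer exposed tends to pull the arms together if the effect wanes off drug. A reader of the valve results would want to know whether a small difference reflects the drug or the share of subjects no longer taking it. The plan equips its cardiovascular endpoints to answer that question and leaves the valve and pressure endpoints without it, although dosing dates and echoes are both collected.

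**Working it through.** The plan states no sample size, power, margin, valvulopathy rate or drug-stopping rate for any echo endpoint, so it has no figure to reproduce.

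**Inputs from the documents**
- Echo subset of about 3,600 (protocol 9.5.1.5) and 1:1 allocation: about 1,800 per arm before exclusions and missing echoes.
- Two-sided 0.05 for secondary endpoints (protocol 9.7.1.6).
- 5% annual drop-out (protocol 9.7.2). This is a study drop-out rate used for the event-driven sample size, not a rate of stopping drug.

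**Assumptions not in the documents**
- Placebo incidence p0 = 2%, on-drug odds ratio 2.0, and 1,700 evaluable per arm.
- A share q off drug at the echo, equal in both arms.
- A fraction f of the excess risk that persists after stopping.

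**Formulas**
- On-drug odds = 2 × 0.02/0.98 = 0.0408, so p1 = 0.0408/1.0408 = 0.0392 and the excess is 0.0192.
- ITT risk = p0 + (p1 − p0) × (1 − q(1 − f)).
- Example, q = 20%, f = 0: 0.02 + 0.0192 × 0.80 = 0.0354; odds 0.0367; odds ratio 0.0367/0.0204 = 1.80.
- Power is by the two-proportion normal approximation, with 1,700 per arm for ITT and 1,700 × (1 − q) per arm for a simple on-drug comparison.

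| Off drug (q) | Persisting (f) | ITT odds ratio | ITT power | On-drug power (odds ratio 2.0) |
|---|---|---|---|---|
| 0% | n/a | 2.00 | 91.1% | 91.1% |
| 5% | 0 | 1.95 | 88.6% | 89.7% |
| 20% | 0 | 1.80 | 78.0% | 84.1% |
| 20% | 0.5 | 1.90 | 85.6% | 84.1% |
| 20% | 1 | 2.00 | 91.1% | 84.1% |
| 30% | 0 | 1.70 | 68.2% | 79.0% |
| 30% | 0.5 | 1.85 | 82.1% | 79.0% |

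With no persistence, the ITT comparison loses both size of effect and power. With half persisting, the estimate is still attenuated but ITT has more power than the on-drug comparison. With full persistence there is no dilution.

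**Other placebo rates.** Take an on-drug risk ratio of 1.5, 1,800 per arm, q = 20% and f = 0. The ITT risk ratio is 1 + 0.5 × 0.80 = 1.40. Power falls from 48.5% to 34.8% at 2% placebo incidence, from 65.9% to 48.9% at 3%, and from 87.3% to 71.5% at 5%. The undiluted figures hold n at 1,800, so a real on-drug analysis would recover only part of the loss.

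**The case against.** The strongest objection is that a naive on-treatment analysis could itself hide harm. Table 4 schedules echoes at Screening and Months 6, 12, 18, 24, 36 and 48, with none at the EOT visit. A subject who stops because of an abnormal Month 6 echo has no on-drug Month 12 echo. A rule looking only at the Month 12 visit would drop that subject and bias the result towards no harm. This stands, and it shapes the fix.

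The plan's existing sets also do not transfer as written. They are counting and censoring rules for time-to-event endpoints, and SAP Section 8 treats a subject who stops and restarts as still on treatment. That stands too.

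Echo is not singled out: the renal endpoints, conversion to normal glucose and 6-month HbA1c have no on-treatment analysis either. Valve disease and pulmonary hypertension are also reported as adverse events of interest, with Kaplan-Meier curves (SAP 5.6.2). SAP 8.6 takes the most severe echo within a visit window, so a milder off-drug echo cannot displace a worse one in that window. These points soften the concern. They do not close it: the adverse events are investigator-reported, not the comparison read by two blinded central readers, and the window rule ignores drug status. The general rule that safety analyses use the Safety Analysis Set does not help, because that set leaves out only subjects who were never dosed or had no post-dose safety assessment.

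A reader might infer that the ITT analysis must understate valve harm by a known amount, or that the plan would declare valve safety because subjects had stopped drug. The documents support neither. They give no stopping rate or persistence, and they set no echo margin or rule for declaring no valve effect.

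**Conclusion.** The gap is real and worth closing. Every echo comparison is ITT-based, off-drug echoes enter it, and no exposure-based echo comparison is planned. The direction of any dilution is towards no harm, on condition that valve or pressure changes do not fully persist after stopping. Its size cannot be derived from the documents. In the illustration, an on-drug odds ratio of 2.0 appears as 1.95 at 5% off drug and 1.80 at 20%, both with no persistence; at 20% it is 1.90 with half persisting and unchanged with full persistence. The effect may be modest at 1 year and larger at later visits if more subjects have stopped by then, but the later echo endpoints are exploratory. The case for a supplementary analysis rests on an estimate closer to the effect in people taking the drug. It does not rest on power, which can be lower than under ITT.

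**What to change.** In SAP 5.4.3 and 5.8, and in protocol 9.7.1.7 and 9.7.1.8, keep ITT primary and add one supplementary table per echo endpoint:

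- **Eligible echoes:** those taken while the subject is actually taking drug, or within 30 days of the last dose before the echo. State that echoes during longer interruptions are excluded, since the SAP Section 8 definition would admit them.
- **New and worsened valvulopathy:** count an event if any eligible post-baseline echo up to the timepoint is positive; otherwise use the last eligible echo. Subjects who stopped after an abnormal echo then stay in as events.
- **Pulmonary artery systolic pressure:** use the eligible echoes in the planned repeated-measures model.

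The cost is SAP and protocol wording and one table per endpoint; no new visits or data are needed. There are three downsides. The comparison is not fully protected by randomization and may be affected by selective stopping. Subjects who stop early contribute shorter exposure, and those with no eligible post-baseline echo contribute nothing. The any-positive rule also differs from the ITT status at the visit, so the table should say so. It should be read beside the ITT result and not in place of it.

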4 LIST OF ABBREVIATIONS AND DEFINITIONS OF TERMS

(revised per Amendments 01 and 02)

Abbreviation	Term
AACE	American Association of Clinical Endocrinologists
ACE	American College of Endocrinology
ACR	albumin-to-creatinine ratio
ADA	American Diabetes Association
AE	adverse event
ALT	alanine aminotransferase
AST	aspartate aminotransferase
BID	twice daily
BMI	body mass index
BNP	B-type natriuretic peptide
BP	blood pressure
BSA	body surface area
CA	Competent Authority
CAD	coronary artery disease
CEC	Clinical Endpoint Committee
CFR	Code of Federal Regulations
CI	confidence interval
CKD	chronic kidney disease
CKD-EPI	Chronic Kidney Disease Epidemiology Collaboration
CRA	clinical research associate
CRF	case report form
CRO	contract research organization
CV	cardiovascular
CVD	cardiovascular disease
CVOT	cardiovascular outcomes trial
DEA	Drug Enforcement Administration
DMC	Data Monitoring Committee
DPP	Diabetes Prevention Program
eGFR	estimated glomerular filtration rate
ECG	electrocardiogram
EER	Estimated Energy Requirement
EOS	end of study
EOT	end of treatment
ESRD	end-stage renal disease
EU	European Union

Abbreviation	Term
FDA	Food and Drug Administration
FPG	fasting plasma glucose
FWER	family-wise error rate
GCP	Good Clinical Practice
GGT	gamma glutamyl transpeptidase
HbA _{1c}	glycosylated hemoglobin
HDL-C	high density lipoprotein-cholesterol
HF	heart failure
HR	heart rate
hsCRP	high sensitivity C-reactive protein
ICF	informed consent form
ICH	International Conference on Harmonisation
IEC	Independent Ethics Committee
IL	interleukin
IND	Investigational New Drug
IRB	Institutional Review Board
ITT	Intent-to-Treat
IxRS	interactive voice and/or web response system
LDL-C	low density lipoprotein-cholesterol
LFTs	liver function tests
LNH	low/normal/high
LV	left ventricular
MACE	major adverse cardiovascular events
MACE+	MACE or hospitalization for unstable angina or heart failure, or any coronary revascularization
MAOI	monoamine oxidase inhibitor
MedDRA	Medical Dictionary for Regulatory Activities
MI	myocardial infarction
MRI	magnetic resonance imaging
SGTP	sequential gatekeeping testing procedure
NAFLD	Non-Alcoholic Fatty Liver Disease
NKF	National Kidney Foundation
OGTT	oral glucose tolerance test
OTC	over-the-counter
PD	pharmacodynamic
PGx	pharmacogenomics
PH	pulmonary hypertension
PI	principal investigator
PK	pharmacokinetic

Abbreviation	Term
PT	preferred term
QTc	corrected QT interval
RBC	red blood cell
SAE	serious adverse event
SAP	statistical analysis plan
SNRI	serotonin norepinephrine reuptake inhibitor
SOC	system organ class
SOP	standard operating procedure
SSRI	selective serotonin reuptake inhibitor
SUSAR	Suspected, Unexpected, Serious Adverse Reaction
T2DM	type 2 diabetes mellitus
TCA	tricyclic antidepressant
TEAE	treatment-emergent adverse event
TEMAV	treatment-emergent markedly abnormal laboratory values
TIMI	Thrombolysis in Myocardial Infarction
TNF- α	tumor necrosis factor-alpha
ULN	upper limit of normal
US	United States
WBC	white blood cell
WHO DD	World Health Organization Drug Dictionary

